## Background:

Controlling post-operative pain is a standard part of managing any post-operative patient. Laparoscopic Total Extraperitoneal (TEP) Herniorrhaphy is a widely accepted technique to repair inguinal hernias and is offered to patients in our practice. The surgery requires general anesthesia and patients typically experience a significant amount of pain during the first post-operative day, at the incision sites, but more-so in the abdominal wall. Local anesthetics such as Lidocaine and Bupivacaine are commonly used for regional anesthesia in most surgical settings. These agents block the voltage-gated sodium channels of neuronal membranes halting the rate of depolarization or conduction of pain response from pain receptors to the brain. They are widely used, very safe and highly effective. The use of these agents have been described to prevent post-operative pain in laparoscopic surgery for

cholecystectomy, appendectomy and gynecologic surgery. The TEP technique, in contrast to intra-abdominal surgeries, remains entirely in the anterior abdominal wall where a temporary space between the muscle and connective tissue is made to repair the defect and place a piece of mesh. This site of surgical dissection and trauma is a potential target for use of local anesthetics to decrease post-operative pain. There have also been a small number of studies describing the use in laparoscopic hernia repair with contrasting conclusions, three reporting significant reductions in post-operative pain with the use of intraperitoneal anesthetic and four studies suggesting no difference. In addition, these reports are limited by small enrollment sizes in a wide variety of sample populations internationally, (only one conducted in the United States in 1998), using a broad range of analgesia and anesthetic practices. Thus, the utility of local anesthetic in this setting remains at the forefront of debate. Clearly, a prospective, randomized, placebo-controlled study with a larger sample size in a more representative population is needed to draw practice-changing conclusions.

## Objectives:

Primary Objective: To assess effect of local anesthetic into the preperitoneal space during laparoscopic hernia repair on post-operative pain.

#### Recruitment:

The patients will be recruited and consented for the study in the clinics of the above listed General Surgeons. We calculated the sample size required so we have a power of 90% with intention to treat of detecting at least a 27% reduction of pain score with a 2-tailed test at  $P \leq .05$ . This number came to 114. We added 10% to account for possible loss of subjects to achieve an enrollment target of 125.

#### Inclusion Criteria:

- Age  $\geq 18$  with unilateral or bilateral inguinal hernia for laparoscopic repair
- American Society of Anesthesiology (ASA) Class I and II

#### Exclusion Criteria:

- Conversion from laparoscopic to open surgery
- History of chronic pain or ongoing treatment for chronic pain
- Age  $<18$
- Allergy to local anesthetics

#### Human Protection Plan:

##### Informed Consent:

Informed consent will be obtained using attached form following the Standard Operating Procedures for Informed Consent (see attached form SOP#: IC607-S). Consent will be obtained by the principle investigator, co-investigators or the research coordinator. Those subjects unable to read or sign will be consented with a witness and those unable to speak English will be consented with a translator, following Standard Operative Procedures (see attached forms SOP#: IC608-S and SOP#: IC605-S)

##### Adverse effects and unanticipated problems:

Adverse reactions are rare and dose-dependent. Serious reactions are extremely infrequent and preventable with proper dosage calculations. Maximum Dose: 90mg for adult. 0.5% Bupivacaine 5mg/mL with epinephrine. (15 mL, a total of 75mg will be given) .

- Adverse effects of Local Anesthetic:
- Common: (= to 10% or more) None
- Less Common: (= to 3-9%) None
- Rare ( =2% or less) None
- Very Rare: (=1% or less)
  - Local reactions (1.9/10,000) : local paresthesias (sensation of tingling, tickling, burning or numbness)
  - Systemic Toxicity (7.5/10,000)
    - CNS toxicity: perioral/tongue paresthesias, tremors, dizziness, slurred speech, double vision, tinnitus (ringing in the ears), confusion, restlessness, convulsions, seizure
    - Methemoglobinemia
    - Cardiovascular toxicity: bradycardia (slow heart rate), arrhythmias (abnormal rhythm)
    - Allergic reaction: skin redness and swelling, itchy rash, shortness of breath, throat swelling, low blood pressure

All internal adverse effects will be reported to the IRB using the Unanticipated Problem Report (see attached). If serious, this will be reported to the expedited IRB within 10 working days/14 calendar days. If non-serious this will be reported to the full IRB within 20 working days/30 calendar days.

#### Benefit:

Local anesthetics are safe and effective agents widely-used in surgical specialties to induce absence of pain sensation. 0.5% is a standard dose of Bupivacaine used in surgery and will be used in this study. The anesthetic will be instilled through a laparoscopic port trocar into the preperitoneal space, the site of the majority of surgical dissection and location of mesh placement. The risks are almost negligent for local anesthetic as described and maximum doses of 175mg will not be exceeded. The potential benefit is improved post-operative pain, less post-operative stress maximizing patient comfort and recovery while minimizing additional IV and oral analgesics necessary post-operatively.

#### Subject Reimbursement:

None

#### Data Analysis:

We calculated the sample size required so we have a power of 90% of detecting at least a 27% reduction of pain score with a 2-tailed test at  $P \leq .05$ . This was done using the data in our literature review, which described a mean post-operative VAS pain score in the placebo group of 3.57 with a standard deviation of 1.47, and a mean difference between groups of 1.23, calculating the effect size at 0.84 (1.23/1.47). At 90% power and an effect size of 0.84, a total of 64 total patients is needed for significant conclusions in a parallel study, 32 in each arm. We added 10% to the total sample size for intended enrollment to account for potential lost subjects during the trial.

---

Our statistician will provide randomization to the inpatient pharmacy who will provide the OR with the blinded study solution. Statistical data will be based on an intention-to-treat principle. Data collection will be managed by the Research Coordinator and entered in an identifier-free, password-protected database. The Mann-Whitney U test will be applied to data on pain score and analgesia required while Fisher's exact test will be used to calculate association of secondary outcomes.

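### Two sample sizes (114 and 64) are given for the same power claim, and the 64 is sized on a 34.5% reduction, not the stated 27%

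*Combined protocol and SAP*

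**What the plan says.** The Recruitment section claims "a power of 90% with intention to treat of detecting at least a 27% reduction of pain score", two-tailed at .05, and continues: "This number came to 114. We added 10% to account for possible loss of subjects to achieve an enrollment target of 125". It gives no mean, SD or effect size.

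The Data Analysis section makes the same claim, "so we have a power of 90% of detecting at least a 27% reduction of pain score", at the same two-tailed level. It then explains the calculation: "This was done using the data in our literature review". The inputs it takes from there are a placebo mean of 3.57 and an SD of 1.47. For the effect it uses "a mean difference between groups of 1.23, calculating the effect size at 0.84 (1.23/1.47"). It concludes that 64 patients, 32 per arm, are required: "At 90% power and an effect size of 0.84, a total of 64 total patients is needed". It adds 10% for losses but prints no enrolment figure. The planned test for pain score is the Mann-Whitney U test, under intention to treat.

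**The concern.** Power, significance level, sidedness and target reduction are the same in both sections, yet the totals before the loss allowance differ by 50 patients (114 − 64). The only printed derivation leads to 64. The only printed enrolment target, 125, belongs to 114, which has no derivation. A reader cannot tell which total the trial relies on or when recruitment is complete: stopping at about 71 or at 125 could each be defended from the text.

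Data Analysis also presents its calculation as one for a 27% reduction, but the inputs it lists describe a larger one. If 64 is the operative number, the trial has materially less power for its stated target than it claims. If 0.84 is the intended effect, 114 is far more than that effect requires and the excess is not explained.

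**Working it through.** **Inputs.** From Data Analysis: placebo mean 3.57, SD 1.47 (taken as common to both arms, an assumption), difference 1.23, effect size 0.84, 90% power, two-sided .05, 32 per arm. From Recruitment: 114, plus 10%, target 125.

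**1. Reproduce the 64.** 1.23/1.47 = 0.837, which rounds to 0.84. The normal approximation is n per arm = 2(1.960 + 1.282)²/d². With d = 0.837 it gives 30.02, so 31 per arm (62 in total). The t-test (noncentral t) needs 31.01, so 32 per arm (64 in total). Power at 32 per arm is 91% by t-test. It is about 90% by Mann-Whitney, taking the rank test as worth 0.955 of the sample size (normal-shaped data). So 64 is correct for an effect size of 0.84.

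**2. Compare the inputs with 27%.**
- 1.23/3.57 = 34.5%.
- 0.27 × 3.57 = 0.964 points, and 0.964/1.47 = 0.656.
- For 1.23 to be a 27% reduction, the placebo mean would be 1.23/0.27 = 4.56.
- If 3.57 were the treated mean, the reduction would be 1.23/(3.57 + 1.23) = 25.6%, still not 27%.

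**3. Sample size for 27% on the printed inputs** (d = 0.656, 90% power).

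| Method | n per arm | Total |
|---|---|---|
| Normal approximation | 48.9 | 98 |
| t-test | 49.9 | 100 |
| Mann-Whitney, efficiency 0.955 | 52.2 | 106 |
| Mann-Whitney, worst-case efficiency 0.864 | 57.7 | 116 |

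The last two rows divide the t-test figure by the efficiency. None of these is near 64. A total of exactly 114 appears if d is first rounded to 0.66 and the worst-case efficiency is applied (56.97, so 57 per arm), or if the normal-approximation figure is rounded to 49 and inflated by 15% (56.35, so 57 per arm). The documents mention neither step, so these are possible explanations only. From d = 0.84, no variant at 90% two-sided power gives more than 72.

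**4. Power for a 27% reduction** (d = 0.656).

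| Analysed | t-test | Mann-Whitney, 0.955 | Mann-Whitney, 0.864 |
|---|---|---|---|
| 64 | 73% | 71% | 67% |
| 71 | 78% | 76% | 71% |
| 114 | 93% | 92% | 90% |
| 125 | 95% | 94% | 92% |

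Simulating the Mann-Whitney test on normal data (20,000 runs) gave 70% at 32 per arm and 92% at 57 per arm. With 64 analysed, 90% power is reached only for a reduction of 33.9% (t-test) or 34.7% (Mann-Whitney, 0.955). If the true effect size were 0.837, 114 would give about 99% power.

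**5. Loss allowance.** 114 × 1.1 = 125.4, which matches 125. 64 × 1.1 = 70.4, about 71. The allowance therefore does not bridge the two totals.

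**6. Sensitivity.** For a difference of 0.964, 64 patients reach 90% power only if the SD is at most 1.17 (t-test) or 1.14 (Mann-Whitney, 0.955). With SD 1.47 they do so only if the placebo mean is at least 4.48 or 4.59 respectively. The 114 also depends on the inputs: its power falls below 90% once the SD exceeds about 1.57 (t-test) or 1.54 (Mann-Whitney, 0.955). At an illustrative SD of 1.75 it is 83% or 81%.

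**The case against.** The strongest reply is that Recruitment prints the only enrolment target, that 125 agrees with 114 plus 10%, and that 114 gives adequate power for 27% on the printed inputs. The power loss arises only under an enrolment of about 71, which is printed nowhere. This stands as a limit on the consequence: the trial is not shown to be underpowered. It does not remove the conflict, because Data Analysis states without qualification that 64 patients suffice.

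It can also be said that the 27%, the 3.57 and the 1.23 may come from different studies and each be correctly transcribed. Data Analysis attributes 3.57, 1.47 and 1.23 to the literature review and states the 27% separately. That is fair: what is established is that the figures cannot describe one comparison, not which of them is wrong. Data Analysis nevertheless uses them together as one calculation.

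The words "at least" in the power claim do not help, since 90% power for 27% or more requires the calculation to be done at 27%. Nor does the reference to intention to treat in Recruitment, because Data Analysis adopts the same principle and each section adds its own 10%.

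Finally, the reconstruction of 114 depends on rounding and on an allowance the documents never mention. That is right, and the conclusion does not rely on it.

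**Conclusion.** The concern holds and needs correcting. One power claim carries two unreconciled totals, and the derivation printed in Data Analysis powers a 34.5% reduction rather than 27%. The 64 is not a miscalculation for an effect size of 0.84; the error lies in presenting it as the number for 27%.

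With 3.57 and a common SD of 1.47 as printed, the chance of missing a true 27% reduction with 64 analysed is about 27–30%, against the stated 10%. With 114 analysed it is about 7–8%, or about 10% at worst-case rank-test efficiency. These figures all rest on the printed mean and SD, and the documents cannot show whether those are right because the literature data are not reproduced. The contradiction between the sections does not depend on them.

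**What to change.** The sponsor should state which total governs, then use one total, one set of inputs and one enrolment target in both sections.

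- **If 125 governs**, replace the 0.84, 64 and 32 per arm in Data Analysis with text such as:

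> A 27% reduction from a placebo mean of 3.57 is 0.96 points; with a common SD of 1.47 the effect size is 0.66. With 114 patients analysed (57 per arm), the Mann-Whitney test at two-sided .05 has about 92% power, assuming approximately normal scores. Target enrolment is 125.

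  Add how 114 was obtained, including any allowance made for the rank test. This is wording only and needs no patients beyond the printed target.

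- **If 64 governs**, state about 90% power for a 34–35% reduction and about 70–73% for 27%, print the enrolment figure (about 71), and correct the 27%, 114 and 125 in Recruitment. The cost is giving up the 90% claim for a 27% reduction.

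- **If 3.57 or 1.23 is a misprint**, correct it and recompute the effect size, total and enrolment target in both sections.

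In each case, identify the source of the mean, SD and difference, and say whether they come from one comparison.

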Appendix:

- Informed Consent Form
- Standard Operating Procedures Informed Consent
- Standard Operating Procedures Informed Consent Unable to sign/speak
- Standard Operating Procedures Informed Consent Non-English Speaking
- Unanticipated Problem Report Form
